Each part of the study will include a Screening period of up to 28 days, a study intervention period consisting of 21-day cycles of M8891 single agent (Part 1) and M8891 combined with cabozantinib (Part 2), an End of Study Intervention visit (within 7 days), and a Safety Follow-up period of 30 (\pm 7) days. Subjects who discontinue study intervention for any reason will complete the End of Study Intervention and Safety Follow-up visits. In Part 2A, before Cycle 1 of all dose levels, subjects will receive a single dose of M8891 in the morning in fed conditions (Day -1, Cycle 1) and the PK profile of M8891 will be evaluated pre-dose, 1, 2, 3, 4, 6, 8 and 24h (Day 1, Cycle 1) after administration (Section 5.1.3.2.1). Subsequently on Day 1 Cycle 1, subjects will initiate

treatment with M8891 combined with cabozantinib QD orally every morning under fasted conditions.

Study duration per subject is approximately 8 months for Part 1, and 12 months for Part 2 including screening, treatment and follow up.

[figure not shown]
The design of this study is presented in

Figure 1 and a detailed Schedule of Assessments (SoAs) is provided in Table 1, Table 2, Table 3, Table 4, and Table 5.

Figure 1

Study Design

AE: Adverse event; DL: Dose level; FBE Free-base equivalent; MTD: Maximum tolerated dose; QD: Once daily; SMC: Safety Monitoring Committee; RP2D: Recommended Phase 2 Dose; mRCC: metastatic renal cell carcinoma; **CCI** [REDACTED].

- a. The MTD of M8891 single agent will be defined, and RP2D of M8891 single agent suggested, by the SMC.
- b. Subjects should have progressed to 1 or more previous lines of systemic anticancer therapy, excluding treatment with cabozantinib.
- c. Cabozantinib will be given at the approved 60 mg FBE daily dosage with dosage adjustments to 40 mg or 20 mg permitted to manage AEs.

CCI [REDACTED]

CCI [REDACTED]

- f. 30 subjects evaluable for response.
- g. The DLT assessment period for Part 2A is the Cycle 1 (= 22 days, 21 days of M8891 combined with cabozantinib, preceded by 1 day of M8891 alone) of study treatment. The rest of the Cycles in Part 2A are 21-day cycles of M8891 combined with cabozantinib.
- h. See Section 8.5.1 for the Bayesian two-parameter logistic regression model.

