8.5 Description of Statistical Analyses

8.5.1 General Considerations

The following summary statistics will be used to summarize the trial data per Part and dose level unless otherwise specified:

- Continuous variables: number of not missing observations, mean, standard deviation, median, minimum, and maximum
- Categorical variables: frequencies and percentages.

All summary statistics will be described in detail in the respective Integrated Analysis Plan. There is no formal significance level for this trial and all analyses are considered descriptive.

The cutoff for the analysis will be as follows:

For the analysis after the end of Part 1, the cutoff will be Last Subject Last Visit (LSLV), or 4 months after the last subject enrolled into the monotherapy dose escalation cohort has finished their DLT period, whichever comes first.

For both dose escalation parts, the analysis will focus on the number of subjects experiencing a DLT. The SMC will receive results of a Bayesian two-parameter logistic model with overdose control updated with the observed DLT data for SMCs dedicated to dose escalation decisions ([Babb 1998; Neuenschwander 2008](#)). Recommendation is based on a loss function (probabilities of being in one of the four toxicity probability intervals will be multiplied with a loss term as follows:

$$0 * P(\text{target dosing (0.17-0.33)}) + 1 * P(\text{for over (0.33-0.67] or under dosing [0-0.17]}) + 2 * P(\text{excessive dosing (0.67-1]}).$$

Glossary:

(x.xx-y.yy] = lower limit excluded, upper limit included in the penalties
[x.xx-y.yy] = lower limit included, upper limit included in the penalties

In addition, only doses that have a corresponding probability of less than 25% that the true DLT rate is more than 33% (overdose control) are recommended by the model. The recommended dose level from the Bayesian model for the next cohort is the dose with the lowest loss function from all doses fulfilling the overdose control rule.

- MTD definition

The target DLT rate for the MTD definition is 30%. The MTD suggested by the model (if reached) will be defined as follows:

Highest tested dose with estimated DLT rate $\leq 30\%$. Additionally, the following needs to be fulfilled:

- The upper bound of the 95% credible interval of a potential MTD is not more than 40% and
- The estimated DLT probability for the suggested MTD is above or equal to 17%.

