The purpose of this Integrated Analysis Plan (IAP, referred to as Statistical Analysis Plan in protocol version 2.0 of this study) is to document technical and detailed specifications for the final analysis of data collected for protocol MS1000015-0019. Results of the analyses described in this IAP will partly be included in a Clinical Study Report (CSR) or a separate report (e.g. PopPK analysis). Additionally, the planned analyses identified in this IAP may be included in regulatory submissions or future manuscripts. Any post-hoc, or unplanned analyses performed to provide results for inclusion in a CSR but not identified in this prospective IAP will be clearly identified as such in the CSR.

This IAP does not describe the analyses done for the Safety Monitoring Committee (SMC) meetings. Instead, details can be found in SMC IAP, version 1.0 dated Oct 2017.

The IAP is based upon Section 8 (Statistics) of the trial protocol and is prepared in compliance with ICH E9.

5 Objectives and Endpoints

	Objective	Endpoint	IAP Section
Primary Objective	To determine the maximum tolerated dose (MTD) of M8891 as a single agent in subjects with solid tumors.	Dose limiting toxicities (DLTs) during the first 21-day treatment cycle, based on a predefined set of adverse events (AEs), to determine the MTD.	• 15.1
	To evaluate the safety profile and tolerability of M8891 as a single agent	Incidence and severity of treatment- emergent adverse events (TEAEs), and deaths, including cause of death, from screening up to the End of Treatment visit (EOT).	141516.1
Secondary Objectives		Changes in clinical laboratory measures, electrocardiogram (ECG) measures, vital signs, Eastern Cooperative Oncology Group Performance status (ECOG PS).	
	 To investigate the pharmacokinetic (PK) profile of M8891 as single agent 	 PK parameters of M8891 after QD and BID dosing, as applicable: Cmax, tmax, AUC0-t, AUC0-∞, AUC0-т, t1/2, λz, CL/F, CLss/F, Vz/F, Racc(AUC₁) and Racc(Cma_x) 	

	Objective	Endpoint	IAP Section
	To assess the antitumor activity of M8891 as single agent according to RECIST v1.1	Best overall response (BOR: complete response [CR], partial response [PR], stable disease [SD] or progressive disease [PD]) according to RECIST v 1.1. criteria as assessed by investigators	
		 Clinical benefit defined as CR, PR, and SD for ≥ 12 weeks 	

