CCI	To determine the recommend Phase II dose (RP2D) as single agent.	 PFS (progression-free survival) defined as the time from first study drug administration to either first observation of PD (as assessed by RECIST v 1.1) or occurrence of death due to any cause, whichever occurs first 	
CCI			

The analyses of the endpoints will be described in the respective sections for efficacy, safety or other endpoints, regardless if the endpoint is a primary endpoint or not.

6 Overview of Planned Analyses

During the study, tables, listings and figures (TLFs) and dosing recommendations based on the Bayesian Logistic Model (BLM) will be provided to the SMC. These analyses are described in the separate SMC IAP.

Unless there is a protocol amendment to include more than monotherapy dose escalation in this study, there won't be a further interim analysis, and the main statistical analysis for the monotherapy dose escalation of the study is described within this IAP. This analysis will take place when dose escalation is completed (data cutoff see Section 9); after study completion (i.e. after last subject last visit, when all subjects terminated treatment) an update of the analysis will be provided. If combination dose escalation or expansion parts are added to the study after completion of the dose escalation part, this IAP will be amended.

A data review meeting (DRM) will be held prior to database lock. In addition, no database can be locked until this IAP has been approved.

7 Changes to the Planned Analyses in the Clinical Trial Protocol

In protocol Section 8.5.3.3, estimation of posterior probabilities for clinical benefit and disease control rate are mentioned. These analyses are only applicable for expansion cohorts, and may be performed accordingly at a later time point. For the end of monotherapy dose escalation, only confidence intervals will be presented for the clinical benefit rate.

8 Protocol Deviations and Analysis Sets

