8.2 Definition of Analysis Sets and Subgroups

For purposes of analysis, the following populations are defined in Table 1.

Table 1 Analysis Sets

Population	Description
Screening	All participants who sign informed consent
Dose Escalation	All subjects treated in dose escalation cohorts who did not miss >4 cumulative days planned doses of M8891 in the first cycle of the dose escalation part for other than safety reasons
Safety	The Safety Analysis Set will include all subjects who receive at least one dose of trial treatment.
Pharmacokinetic CCI	All subjects from the safety analysis set without major protocol deviations/violations or events that would affect PK. Subjects in the PK analysis set must have received at least 1 dose of M8891 and have sufficient M8891 plasma concentration data to enable the calculation of at least one PK parameter. Sufficient concentration data is defined as at least 3 valid, post-dose concentration points in the PK profile to obtain any PK parameter.
CCI	

PK Pharmacokinetic; WBC White blood cell.

9 General Specifications for Data Analyses

All tables and listings (and titles and footnotes for figures) will be produced using the Courier New font with a font size of 10 points. A font size of 9 points will be acceptable in cases where a font size of 10 points does not fit.

All TLFs will be produced using a paper size of US letter in landscape with 1 inch margins on all four sides.

Significance level:

There is no formal significance level for this trial and all analyses are considered descriptive. If confidence intervals or credibility intervals are mentioned, the level will be 95% unless otherwise specified.

Cutoff

For the analysis after the end of dose escalation for monotherapy, the cutoff will be 22 days after the first treatment day of the last subject enrolled into the monotherapy dose escalation cohort.

Pooling of centers:

Because of the anticipated small number of subjects enrolled in each center data will be pooled across centers, and the factor center will not be considered in statistical models or for subgroup analyses.

Definition of baseline:

In general, the last non-missing measurement prior to first trial drug administration will be used as the baseline measurement, unless otherwise specified (e.g. Section 15.7).

Definition of duration:

Duration in days will be calculated by the difference of start and stop date + 1 day (e.g. survival time (days) = date of death – date of first treatment + 1).

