15.2 Adverse Events

All adverse events analyses will be based on the safety population.

An AE is any untoward medical occurrence in a subject or clinical investigation subject administered a pharmaceutical product, which does not necessarily have a causal relationship with the treatment. An AE can therefore be any unfavorable and unintended sign (including a laboratory finding), symptom or disease temporally associated with the use of an IMP, whether considered related to the IMP or not. All AEs will be coded using the most recent Medical Dictionary for Regulatory Activities MedDRA version, Version 20.1 or later.

A treatment emergent adverse event (TEAE) is defined as an AE that begins or worsens after at least one dose of the IMP has been administered. AEs that started before administration of IMP or more than 30 days after last dose of IMP will not be considered TEAEs.

Every AE listing will include the following information:

- System organ class (SOC) and preferred term (PT)
- Start and end date/time
- Days under treatment
- Duration
- Seriousness criteria
- Relationship with M8891
- Common Terminology Criteria for Adverse Events (CTCAE) toxicity grade
- Other causality factors
- Action taken with M8891
- Other actions taken
- Outcome
- Whether AE is dose-limiting toxicity

There will be a listing of all AEs, sorted by SOC and PT.

The following summaries will be presented by dose group and overall using the safety population:

- Number of subjects with the following kinds of TEAEs:
 - Any TEAE
 - Related TEAEs
 - TEAEs leading to withdrawal of trial drug
 - o TEAEs leading to death (overall and by reason for death)
 - Serious TEAEs
 - o Related serious TEAEs
 - TEAEs with CTCAE grade ≥ 3
 - o Related TEAEs with CTCAE grade ≥ 3
 - TEAEs leading to dose reduction
 - o TEAEs leading to temporary interruptions of trial drug
- TEAEs by SOC and PT
- Serious TEAEs by SOC and PT
- TEAEs leading to withdrawal of trial drug, dose reduction, temporary interruptions of trial drug, and death
- Non-serious TEAEs occurring with incidence in PT greater than 5% in at least one dose group, by SOC and PT

AEs will be summarized by worst severity per subject, using the MedDRA PT as event category and MedDRA primary SOC as Body System category.

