15.4 Clinical Laboratory Evaluation

The safety population will be used for all clinical laboratory evaluations.

All laboratory results (biochemistry, hematology, coagulation, urinalysis, pregnancy test), will be listed by subject and time point. The following information will be included in the listing:

- Sex of subject
- Date/time of sample
- Treatment day
- Result
- Reference range (for continuous variables)
- Flag for values above ("H") or below ("L") the reference range (for continuous variables)
- Change from baseline (for continuous variables)
- NCI-CTCAE grade
- Flag for value with worst-on trial grade ("Y")

All continuous laboratory results will be summarized by dose and time point, including absolute values and change from baseline.

Laboratory results will also be classified by Grade according to NCI-CTCAE. The worst post-baseline on-trial Grades will be summarized, as well as the worst post-baseline Grades within the first cycle. Shifts in toxicity grading from first treatment to highest Grade will be displayed: number of subjects with shift to any higher grade, to higher grade 3 or 4, to higher grade 4.

Results for variables that are not part of NCI-CTCAE will be presented as below, within, or above normal limits. Only subjects with post-baseline laboratory values will be included in these analyses.

D-dimer results will be listed with biochemistry.

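### At the SAP's main Part 1 cutoff, crude TEAE percentages by dose group rest on very unequal follow-up and can understate incidence in the last-enrolled dose groups

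*SAP*

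**What the plan says.** SAP 15.2 introduces the TEAE tables with "The following summaries will be presented by dose group and overall using the safety population". They count subjects with any, related, Grade 3 or higher, and serious TEAEs, and those leading to withdrawal, dose reduction, interruption or death. SAP 9.2 bases percentages on the number of subjects in the analysis set. The window is open-ended on treatment: "AEs that started before administration of IMP or more than 30 days after last dose of IMP will not be considered TEAEs". Part 1 treatment continues until progression, unacceptable toxicity or withdrawal (protocol 5.1.3.1).

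The two documents give different cutoffs for this analysis:

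- SAP section 9: "the cutoff will be 22 days after the first treatment day of the last subject enrolled into the monotherapy dose escalation cohort".
- Protocol 8.5.1 (repeated in 8.6.1): the last subject's last visit, or "4 months after the last subject enrolled into the monotherapy dose escalation cohort has finished their DLT period, whichever comes first".

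The SAP is version 1.0 of April 2018 and was written for an earlier protocol; it describes itself as "referred to as Statistical Analysis Plan in protocol version 2.0 of this study". SAP section 6 calls the analysis at the end of escalation the main one and adds: "after study completion (i.e. after last subject last visit, when all subjects terminated treatment) an update of the analysis will be provided".

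SAP 15.4 gives laboratory grades a fixed-window summary, "as well as the worst post-baseline Grades within the first cycle". DLTs (SAP 15.1) are also a first-cycle analysis, and the QTcF model (SAP 15.7) has a first-cycle run. No TEAE table has an equivalent.

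**The concern.** A crude percentage of subjects with an event depends on how long they were watched. When cohorts are enrolled one after another and all are cut on the same calendar date, early cohorts have had months to accumulate events and the last has had little more than one cycle. Tabulated side by side, equal toxicity appears as lower incidence in the late-enrolled groups, and a true rise with dose can be masked.

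This bears on interpretation because protocol 5.1.3.3 says that the single-agent RP2D draws on DLTs together with other safety information. Columns by dose group invite reading across doses even though nothing is formally tested.

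**Working it through.** **The plan's own figure.** The Part 1 size scenario (protocol 8.1.1) is 5×3 + 2×6 + 1×9 = 36 evaluable subjects, which reproduces. It is not in dispute.

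**Possible follow-up at cutoff.** From protocol 5.1.3.1: cohorts of 3, the first subject 7 days ahead of the other two by default, and a 21-day DLT period. The fastest default interval between cohorts is 7 + 21 = 28 days, ignoring SMC review time. For eight cohorts (eight projected doses, one cohort each), counting back from the last:

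- SAP cutoff, 22 + 28k days for k = 0 to 7: 22, 50, 78, 106, 134, 162, 190, 218.
- Protocol 4-month limit, 21 + 4×30.4375 = 142.75, about 143 days, plus 28k: 143 to 339.

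The first subject of each cohort has 7 days more. The 36-subject scenario implies 5 + 4 + 3 = 12 cohorts, for which the SAP range would be 22 to 22 + 28×11 = 330 days. Slower enrolment widens it; a shortened stagger, which the SMC may choose, narrows it.

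**Expected crude incidence with equal hazard at every dose.** Assumptions not in the documents: 20% risk of a first TEAE by Day 21; exponential time on treatment with a median of 12 weeks (84 days).

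Constant hazard: h = −ln(0.8)/21 = 0.010626 per day; k = ln 2/84 = 0.008252 per day. The TEAE window is w = min(time on treatment + 30, c), where c is possible follow-up. Expected incidence is:

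- c ≤ 30: 1 − exp(−hc)
- c > 30: 1 − exp(−30h) × [k/(h+k) + (h/(h+k)) × exp(−(h+k)(c−30))]

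Last cohort, SAP cutoff: 20.8% at 22 days (two subjects) and 26.5% at 29 days (first subject); mean 22.7%, about 23%.

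First cohort, SAP cutoff, c = 218: 1 − 0.7270 × [0.4371 + 0.5629 × 0.0288] = 67.0%, about 67%.

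Front-loaded hazard (Weibull shape 0.5): cumulative hazard λ√t with λ = −ln(0.8)/√21 = 0.04869. The last cohort has 20.4% at 22 days and 23.1% at 29 days, mean about 21%. The first cohort is averaged over time on treatment.

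| Cutoff | Hazard | Last cohort | First of 8 |
|---|---|---|---|
| SAP, 22 days | constant | 23% | 67% |
| SAP, 22 days | front-loaded | 21% | 40% |
| Protocol, 4-month limit | constant | 64% | 68% |
| Protocol, 4-month limit | front-loaded | 38% | 41% |
| Update after last visit | constant | 68% | 68% |
| Update after last visit | front-loaded | 42% | 42% |

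**Sensitivity.** Varying Day 21 risk over 10–30% and median treatment over 6, 12 and 26 weeks, the gap at the SAP cutoff runs from 8 points (11% vs 19%) to 54 points (for example 34% vs 88%). At the protocol cutoff it runs from nil to 15 points (45% vs 60%, at 10% risk, constant hazard and 26-week median treatment).

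**Cycle 1 table.** Every subject treated by the SAP cutoff has at least 22 days of possible observation, and the TEAE window extends 30 days past the last dose. Days 1–21 are therefore covered for all, and equal hazards give equal expected incidence (20% in every group here).

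**Would a rate per patient-month solve it?** Not alone. With the front-loaded hazard above, subjects with a first event divided by months at risk is 0.204/0.622 = 0.33 per month at 22 days, but 0.509/4.42 = 0.12 per month at 7 months. Identical toxicity would then look nearly three times worse in the last cohort.

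**The case against.** Much of the case on the other side stands.

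- **The 22-day rule is out of date.** The current protocol's cutoff is later, and in the worked example it shrinks the gap to 3–4 points, against 33 points for one subject in a group of three. The SAP supplied has nevertheless not been aligned, so the short cutoff is still what it specifies.
- **An update is planned.** After the last visit no subject is administratively truncated. That update follows the main escalation analysis, and any real difference in time on treatment between doses would still be unadjusted.
- **Readers can see the imbalance.** Duration of therapy by dose group (SAP 13), disposition by cycle (SAP 10.1) and days under treatment in the AE listings (SAP 15.2) reveal it, but do not correct the percentages.
- **Everything is descriptive.** True, and no test is affected. Descriptive columns still shape judgement.

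A reader might infer more than the documents support:

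- *That the RP2D will be biased.* The SMC decides it, reviews data after each cohort, and works from a separate analysis plan that we do not have (SAP section 4). Nothing shows that the 15.2 tables drive the choice.
- *That the highest doses will look safest.* The SMC may de-escalate or expand a dose (protocol section 2), and at least 6 subjects are needed at the MTD/RP2D, so a dose group may mix early and late entrants. A higher true hazard could also outweigh the shorter follow-up.
- *That the bias is large under either cutoff.* That would require early subjects to be observed for most of the study duration ("Study duration per subject is approximately 8 months for Part 1"). TEAE collection stops 30 days after last dose, so a subject off treatment by about Day 113 (143 − 30) is fully captured at the protocol's 4-month limit.

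**Conclusion.** The concern holds in limited form. At the SAP's cutoff, the crude all-cycle TEAE tables put very unequal follow-up side by side, roughly tenfold across eight cohorts at the fastest default pace. With equal hazards, the last-enrolled groups' TEAE, Grade 3 or higher, and serious TEAE percentages can be understated by tens of points: about 23% against 67%, or 21% against 40%, in the worked example. The follow-up days come from protocol timings; the incidences rest on assumed event risk, hazard shape and treatment duration.

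Under the protocol's cutoff the gap is usually small, though it can reach about 15 points if treatment is long and events are spread out. It affects the main analysis, not the later update as regards truncation, and not the DLT endpoint, whose window is a fixed 21 days. The change is worth making because it is cheap and the like-for-like summary already exists for laboratory grades; it does not call the dose-finding method into question.

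**What to change.** 1. Reconcile the cutoff in SAP section 9 with protocol 8.5.1 and 8.6.1, so that one rule governs the end-of-escalation analysis.
2. In SAP 15.2, add tables by dose group of any, related, Grade 3 or higher, and serious TEAEs with onset in Cycle 1 (Days 1–21), matching the first-cycle summary in SAP 15.4. State that these are for reading across doses.
3. Keep the all-cycle crude tables for late and cumulative toxicity, and show duration of therapy by dose group next to them. Exposure-adjusted rates may be added as supporting output only, with a note that they assume a constant hazard.

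The cost is SAP wording and a few extra tables from AE and dosing dates already collected. The Cycle 1 tables do not show late toxicity, so they supplement the all-cycle tables and cannot replace them.
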